**Other Assessments:**

- Hair quality assessment including normalization of exclamation point hairs and hair shedding will be described.
- Vellus and Indeterminate scalp hair will be described.
- Non-scalp hair assessments (body and nasal hair) will be described.

**Pharmacokinetic:**

The concentration of ATI-502 in the blood predose at Visit 2 and at trough at Visit 4, Visit 6 and Visit 9 will be measured by a bioanalytical lab using fully validated analytical methods.

**Safety:**

- Safety variables to be assessed include: adverse events, clinical laboratory tests (hematology, clinical chemistry, and urinalysis), vital sign measurements (systolic and diastolic blood pressures, respiration rate, heart rate, and oral body temperature), and electrocardiograms.

**Statistical Methods:****Sample Size/ Power Calculations**

The planned sample size is approximately 95 enrolled subjects with approximately 45 subjects enrolled with AT or AU. The sample size estimate was based on published results from a similar study (Crispin et al. 2016) where 32% of subjects receiving active drug achieved at least a 50% relative reduction in hair loss (SALT50) under similar conditions. For the current study, the primary efficacy analysis is mean % change in hair loss, evaluated using SALT scores. That analysis is expected to have greater statistical sensitivity than the SALT50 responder analysis, which is also a secondary efficacy analysis in the current study.

We assume the pooled results of 600mg and 800mg treatment groups in the current study will achieve the same or higher SALT50 response rate (32%) as the published results above, and pooled Vehicle plus 400mg treatment groups will not achieve more than a 6% SALT50 response rate. Based on a comparison of those two pooled groups, the current study is anticipated to have no less than 80% power with a 10% subject dropout rate for the SALT50 analysis. Because the primary efficacy analysis of mean percent reduction in hair loss using SALT scores is expected to be more sensitive than the SALT50 responder analysis, the power for the primary analysis is also expected to be no less than 80%.

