
Methodology:
 
This Phase 2, multicenter, randomized study will evaluate the safety, tolerability and efficacy of ATI-501 for the treatment of AA, AU, or AT in adult subjects. Subjects will be required to have a clinical diagnosis of stable AA, AU, or AT with 30% to 100% total scalp hair loss for a duration of at least 6 months up to and including 12 years. A total of 80 subjects will be randomized with approximately 40 subjects enrolled with AU or AT. Subjects will be randomized to a 1:1:1:1 ratio:
 
 
ATI-501 Oral Suspension, 400 mg, BID for 24 weeks (6 months)
 
ATI-501 Oral Suspension, 600 mg, BID for 24 weeks (6 months)
 
ATI-501 Oral Suspension, 800 mg, BID for 24 weeks (6 months)
 
Placebo Oral Suspension, BID for 24 weeks (6 months)
 
 
During the screening period, subjects will be assessed for eligibility into the study. Subjects qualifying for protocol treatment based on the outcome of screening procedures will be randomized to take 400 mg, 600 mg, 800 mg or placebo suspension twice-daily within approximately 30 minutes following morning and evening meals for 24 weeks. Assessment of response to treatment will be performed at Week 4, Week 8, Week 12, Week 16, Week 20, Week 24, and post-treatment Week 28.
	

Safety and tolerability will be evaluated at each study visit by assessment of adverse events, clinical laboratory tests, and vital signs, and at select visits, ECGs will be completed.

Subjects who complete study visits through Visit 9 will have the option to roll over into an open-label study ATI-502-AA-203. Subjects who withdraw consent or meet study medication discontinuation criteria (Section 3.4.1.2) on study ATI-501-AUAT-201 will not be eligible for roll-over to study ATI-502-AA-203. Subjects who complete the assessments for Visit 9 and then meet study ATI-502-AA-203 entry criteria and provide written consent will skip post-treatment Visit 10. Subjects who are not eligible for ATI-502-AA-203 or who decline to participate should return for the final Visit 10 assessments.

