**Statistical Methods**

The primary efficacy variable will be the percent change from Baseline in the SALT score at Week 24 (Visit 9). This represents the percentage of hair regrowth. It will be calculated as the change from baseline (Visit 2) to Week 24 (Visit 9), divided by the baseline and expressed as a percentage.

Missing data for the primary endpoint will be imputed using Last Observation Carried Forward (LOCF) methodology. The analysis will be conducted on the percent change from baseline over time including all visits using a mixed effect model repeated measures (MMRM). The adjusted mean (LS Mean) for percent change from baseline in the SALT score at each visit, estimated from the MMRM, with the estimated standard error and 95% confidence interval (CI), will be presented in tabular and graphic format. The difference in the adjusted means between treatment groups and the associated 95% CI of the difference will be provided. No adjustment for multiplicity will be made. The model

will include fixed effect terms for treatment, study visit, baseline SALT score group (<50, >=50), and treatment by baseline SALT group interaction. The primary analysis will be based on the Intent-to-Treat (ITT) population. Statistical significance for primary efficacy endpoint will be declared if at least one treatment group comparison at the Week 24 visit has a two-sided p-value less than or equal to 0.05.

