### 1.1. Overview of Alopecia Areata

Alopecia areata (AA) is an autoimmune dermatologic condition, which, in its mildest form, is typically characterized by patchy non-scarring hair loss on the scalp and/or body. More severe forms of AA include total scalp hair loss, known as alopecia totalis (AT), and total loss of all the hair on the scalp and body- importantly, including loss of eyebrows, eyelashes, and intranasal hair- known as alopecia universalis (AU). While spontaneous regrowth of hair is common in the milder form of AA (patchy), where the hair loss may wax and wane, in patients with the extensive hair loss of AT or AU, spontaneous hair regrowth is rare. AA affects both males and females across all ethnic groups and ages, and with a lifetime risk of 1.7% (Safavi 1995). About two-thirds of affected individuals are 30 years old or younger at the time of disease onset.

The course of AA is unpredictable and while up to 50% of patients may recover within 1 year even without treatment, most patients will have more than one episode of hair loss (Price 2008). Factors portending a poorer prognosis for regrowth are more extensive hair loss presentations (extensive AA, AT, AU), an ophiasis pattern of hair loss, a long duration of hair loss, a positive family history, the presence of other autoimmune diseases, nail involvement, and young age of first onset (Tosti 2006, Weise 1996). In children, the disease may have a tendency towards worsening with time even if the initial presentation was mild, and the progressively disfiguring nature of the disease can be psychologically devastating. AA is highly associated with numerous psychiatric comorbidities including adjustment disorders, anxiety disorders and depression in both children and adults, and an effective treatment for AT and AU, the more severe forms of the disease, represents a significant unmet medical need (Bilgic 2014, Ruiz-Doblado 2003, Alkhalifah 2010).

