## **5.7. Randomization and Blinding**

Prior to the start of the study, Aclaris Therapeutics, Inc. or a designated third party will generate a list of randomization numbers that shall be transmitted to the assigned clinical packaging organization for study medication labeling. The randomization list will be stored with access limited to designated personnel for study medication labeling. The randomization list will be made available, as appropriate, to unblind the database.

Subjects will be assigned to 1 of the 4 treatment groups in a random manner and at a 1:1:1:1 ratio. At Baseline (Visit 2), an investigational center staff member will assign study medication to eligible subjects by selecting an appropriate Subject Kit as detailed in the Pharmacy Manual.

Blinding of study medication is important for validity of this study. This study uses a double-blind design. The study medications are indistinguishable in appearance, as packaged and labeled.

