### **4.2. RANDOMIZATION AND BLINDING**

Prior to the start of the study, Aclaris Therapeutics, Inc. or a designated third party will generate a list of randomization numbers that shall be transmitted to the assigned clinical packaging organization for study medication labeling. The randomization list will be stored with access limited to designated personnel for study medication labeling. The randomization list will be made available, as appropriate, to unblind the database.

In the treatment period, subjects will be assigned to 1 of the 4 treatment groups in a random manner and at a 1:1:1:1 ratio. At Baseline (Visit 2), an investigational center staff member will assign study medication to eligible subjects by selecting an appropriate Subject Kit. The staff member must select Subject Kits in chronological sequence and in an ascending numerical order starting with the lowest available Subject Kit number. No Subject Kit number may be omitted or reused. The Subject Kit number is the randomization number.

This study uses a double-blind design. The study medications are indistinguishable in appearance, as packaged and labeled.

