### **4.3. HANDLING OF DATA**

#### **4.3.1. Strata and Covariates**

No stratified analyses are planned.

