### **6.2.2. Primary Efficacy Analysis**

Descriptive statistics for the SALT score, change, and percent change from baseline will be presented by analysis visit. Percent change from baseline in SALT over time up to Week 24 will be analyzed using a mixed effect for repeated measures (MMRM) model. This primary analysis will utilize the score with imputation for LOCF and will be based on the ITT population. The model will include fixed effect terms for treatment, study visit, and treatment by study visit interaction. Within-subject variability will be modeled using a compound symmetry covariance structure. The least squares mean (LS Mean) percent change from baseline in the SALT score at each visit, estimated from the MMRM model, with the estimated standard error and 95% confidence interval (CI), will be presented in tabular and graphic format. The difference in the adjusted means between treatment groups and the associated 95% CI of the difference will be provided.

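### AT/AU status is an enrolment target and a named prognostic factor, yet no stratification by it is described and neither primary model contains it, so a chance imbalance shifts the Week 24 dose estimates

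*Protocol*

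**What the plan says.** **Mix of types.** Protocol Synopsis, Sample Size: "The planned sample size is approximately 95 enrolled subjects with approximately 45 subjects enrolled with AT or AU". Protocol 9.1 and SAP 4.1 give the same target. The Synopsis Methodology paragraph still has a different one: "A total of 80 subjects will be randomized with approximately 40 subjects enrolled with AU or AT". Either way, about half the trial is AT/AU.

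**Prognosis.** Protocol 1.1 says that "in patients with the extensive hair loss of AT or AU, spontaneous hair regrowth is rare", whereas it describes spontaneous regrowth as common in milder patchy disease. It also lists extensive AA, AT and AU together as presentations with a poorer outlook for regrowth.

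**Allocation.** Protocol 5.7: "Subjects will be assigned to 1 of the 4 treatment groups in a random manner and at a 1:1:1:1 ratio". No stratum is named. SAP 4.2 describes a single sequence: "The staff member must select Subject Kits in chronological sequence and in an ascending numerical order starting with the lowest available Subject Kit number".

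**Primary model.** The protocol model (Synopsis and 9.4.1) "will include fixed effect terms for treatment, study visit, baseline SALT score group (<50, >=50), and treatment by baseline SALT group interaction". SAP 6.2.2 says: "The model will include fixed effect terms for treatment, study visit, and treatment by study visit interaction". SAP 4.3.1 adds: "No stratified analyses are planned". SAP section 7 nevertheless states that its analyses agree with the protocol.

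**Other uses of type.** SAP 6.1 tabulates diagnosis type at baseline. The subsets in SAP 6.2.7 are SALT group and episode duration, not type.

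**The concern.** The primary variable is percent regrowth on SALT, and the protocol itself expects regrowth to depend on how extensive the disease is. A factor that splits the trial roughly in half and predicts the outcome is normally balanced at allocation, adjusted for in the model, or both. Here neither document does either explicitly.

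The protocol's one baseline term does not stand in for it. Protocol Tables 5 and 6 define AT/AU as more than 95% scalp hair loss, so every AT/AU subject falls in the ≥50 SALT group together with patchy subjects at 50-95%. The SAP drops even that term.

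Two things are at stake. If one dose arm happens to have fewer AT/AU subjects than placebo, part of the estimated dose effect reflects case mix. The difference between types also stays in the residual and widens every Week 24 interval. Protocol 9.4.1 declares success if any one dose reaches p ≤ 0.05 without multiplicity adjustment, so a single unbalanced arm can matter.

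**Working it through.** **1. The plan's own figure.** Inputs from SAP 4.1: 32% v 6% response, 95 enrolled, 10% dropout, so 95 × 0.9 = 85.5, or about 43 per pooled group. Fisher's exact test at 43 per group has 84.4% power, which matches the SAP's 84%. The stated sample size is not in dispute here, and the change proposed below does not alter it.

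**2. How large a chance imbalance to expect.** This step uses document figures only. Take 45 AT/AU among 95, split at random into arms of 24, 24, 24 and 23. For two arms of sizes n₁ and n₂:

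SD of share difference = √[(45/95)(50/95)(95/94)(1/n₁ + 1/n₂)]

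- 24 v 23: √(0.25196 × 0.08514) = 0.146
- 24 v 24: √(0.25196 × 0.08333) = 0.145

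Exact hypergeometric probabilities of a gap of 20 percentage points or more:

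| Case | Probability |
|---|---|
| One comparison, 24 v 23 | 14.5% |
| One comparison, 24 v 24 | 19.5% |
| At least one of three doses, placebo arm of 23 | 33% |
| At least one of three doses, placebo arm of 24 | 39% |

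The single-comparison figures differ because the counts are discrete: at 24 v 24 a five-subject difference is already 20.8 points. If the Synopsis figures of 40 in 80 applied (20 per arm), the SD would be √[0.25 × (80/79) × (2/20)] = 0.159, slightly larger.

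**3. How much of the imbalance reaches the estimate.** After LOCF each subject has a value at each visit, so the SAP model's Week 24 contrast is essentially the raw difference in arm means, and an imbalance carries through at 100%. This was checked with a null simulation of a Week 24 cross-section. Its assumptions, none from the documents, are a residual SD of 30, a type gap of 10, 20 or 30 points, 15 or 25 patchy subjects with SALT <50, and LS means weighted equally over the two SALT groups for the protocol model.

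| Model | Carry-through of imbalance |
|---|---|
| SAP 6.2.2 | about 100% |
| Protocol 9.4.1 | about 42-62% |
| With a type term | about 0% |

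**4. Error rates in the same simulation.** Over all randomisations, type I error was 3.7-5.7% across the three models. Among trials with an imbalance of 20 points or more, it was about 6-12% under the SAP model and about 3-6% under the protocol model. These conditional rates rest on a small share of the draws and are approximate.

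**5. Size of the shift and the loss of precision.** Assume a within-type SD of 35 and a gap D between types in mean percent change.

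- Shift under the SAP model at a 20-point imbalance = 0.20 × D.
- SE ratio, adjusted to unadjusted = √[35² / (35² + D² × 45 × 50/95²)].

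| D | Shift | SE ratio | SE reduction |
|---|---|---|---|
| 10 | 2 points | 0.990 | 1% |
| 20 | 4 points | 0.962 | 4% |
| 30 | 6 points | 0.919 | 8% |

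**The case against.** **Chance imbalance is not bias.** Randomisation keeps the estimate unbiased on average, and unadjusted intervals already allow for imbalance. This stands. A reader might infer that the omission inflates the false-positive rate; the check above gives about 5% overall. The case for adjusting is precision and a better estimate in the realised trial.

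**The SALT group already adjusts for severity.** Protocol 1.1 groups extensive AA with AT and AU, much as the ≥50 group does. This stands in part. It would be wrong to say that the protocol model cannot correct an imbalance, since it removes roughly half under the assumptions shown. The SAP model, however, contains no such term.

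**The gap is not documented.** Protocol 1.1 speaks of spontaneous regrowth, while eligible subjects need at least 30% loss, at least 6 months' duration and no current regrowth. The plan also assumes at most 6% responders in pooled placebo plus 400 mg. If all of those were patchy, that is 6% × 95/50 = 11.4% of patchy subjects. With SD 35 and a normal distribution, the patchy mean is 50 − 1.21 × 35 ≈ 8 points. If AT/AU averages near zero, the gap in those arms is about 8 points, and a much larger overall gap would have to come from the higher doses. So large gains in effective sample size cannot be claimed from these documents, and the table above is illustrative only.

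**Non-stratification is inferred.** Neither document rules out stratification by type, and Protocol 5.7 refers kit selection to a Pharmacy Manual that is not available here. The single ascending kit sequence makes stratification unlikely. If the list were stratified, the factor would still belong in the model.

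**Imbalance will be visible.** SAP 6.1 tabulates type by arm. That would show an imbalance, but no planned primary-endpoint analysis would correct it.

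**Conclusion.** The point holds as one of precision and of the realised estimate, and a change should be made. An AT/AU imbalance of 20 points or more against placebo is likely enough to plan for: 14.5% to 19.5% for one dose and 33% to 39% for at least one of three. Those probabilities rest only on 45 in 95 and near-equal arms.

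Such an imbalance passes in full into the SAP estimate and in part into the protocol estimate. The consequence of 2 to 6 points, and the SE saving of 1% to 8%, depend on an assumed gap of 10 to 30 points and an SD of 35.

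The documents do not support three stronger readings: that the trial is biased, that both models are equally exposed, or that the protocol establishes a large difference between types in this eligible population.

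**What to change.** Before unblinding, reconcile Protocol 9.4.1 and SAP 6.2.2 into one primary MMRM with these terms:

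- treatment, visit and treatment-by-visit;
- baseline hair-loss type, patchy (30-95%) v AT/AU (>95%), using the rule already in Protocol Tables 5 and 6;
- type-by-visit.

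Report LS means at the observed mix of types. Use the same model for percent change in ALODEX.

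In SAP section 7, replace the statement of consistency with an account of how this model differs from the protocol's SALT-group and treatment-by-SALT-group terms. Keep SALT <50/≥50 as the subset analysis already planned in SAP 6.2.7. Reconcile the Synopsis figure of 40 in 80 with 45 in 95.

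A change to allocation is not proposed. Protocol version 5.0 is dated April 2019 and the last completion is estimated for July 2019, so with 24 weeks of treatment randomisation has probably closed.

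The cost is SAP and protocol wording plus a few degrees of freedom. Baseline SALT is recorded before randomisation for every subject, so no new data are needed.

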**Statistical Methods**

The primary efficacy variable will be the percent change from Baseline in the SALT score at Week 24 (Visit 9). This represents the percentage of hair regrowth. It will be calculated as the change from baseline (Visit 2) to Week 24 (Visit 9), divided by the baseline and expressed as a percentage.

Missing data for the primary endpoint will be imputed using Last Observation Carried Forward (LOCF) methodology. The analysis will be conducted on the percent change from baseline over time including all visits using a mixed effect model repeated measures (MMRM). The adjusted mean (LS Mean) for percent change from baseline in the SALT score at each visit, estimated from the MMRM, with the estimated standard error and 95% confidence interval (CI), will be presented in tabular and graphic format. The difference in the adjusted means between treatment groups and the associated 95% CI of the difference will be provided. No adjustment for multiplicity will be made. The model

will include fixed effect terms for treatment, study visit, baseline SALT score group (<50, >=50), and treatment by baseline SALT group interaction. The primary analysis will be based on the Intent-to-Treat (ITT) population. Statistical significance for primary efficacy endpoint will be declared if at least one treatment group comparison at the Week 24 visit has a two-sided p-value less than or equal to 0.05.

### **Secondary Efficacy Analyses**

A secondary sensitivity analysis of the primary endpoint will be conducted using the PP population. This analysis will use the same methodology as described for the primary analysis just applied to the PP population.

The secondary efficacy endpoints include the change from Baseline in the ALODEX score, ASAA (CR & SR), AFHA (CR & SR), PhGIS, SGIS, AIA, SGSHQ, and DLQI as well as the proportion of subjects achieving a  $\geq 50\%$  hair growth compared with Baseline based upon the SALT score and ALODEX score, separately. SGITS responses at Week 12, 24, and 28 will be summarized. Various secondary responder efficacy endpoints will be defined based upon the SALT score, the ALODEX score and the AAA (Clinician and Subject) questionnaires. Details of these responder definitions will be specified in the statistical analysis plan (SAP). Global Impression of Change (Clinician and Subject) at Week 24 (Visit 9) will be used in the psychometric evaluation of the scores from the ASAA (CR and SR), respectively. Non-Scalp Hair Loss Assessment, Vellus and Indeterminate Hair Assessment and Hair Quality Assessment including normalization of exclamation point hairs and hair shedding will be described. The analysis for percent change in ALODEX score will use the same methodology as specified for the primary efficacy analysis. Other parameters will be analyzed as detailed in the statistical analysis plan.

Data collected in this trial will be used to evaluate the psychometric properties of the newly developed patient-reported and clinician-reported outcome (PRO and ClinRO) questionnaires. A measurement-focused statistical analysis plan will detail the data analytic strategy used to achieve the measurement property and score interpretation objectives. The anticipated psychometric evaluation analyses for the newly developed PRO and ClinRO questionnaires may include the following: score description, score reliability, score construct-related validity and score interpretation.

### **Pharmacokinetic Analyses**

The concentration of ATI-502 in the blood will be summarized (mean [SD], minimum, median maximum) predose at Visit 2 and at trough at Visit 4, 6, and 9.

### **Safety Data**

Safety analyses will include descriptive statistics calculated on the safety parameters using the safety population. The proportion of subjects with treatment-emergent adverse events will be tabulated and presented by treatment and Medical Dictionary for Regulatory Activities (MedDRA) System Organ Class. Vital signs and clinically significant abnormal laboratory results will also be tabulated and presented by treatment group.

Data from all randomized and treated subjects will be presented and summarized. Safety summaries by study treatment group will include listings by study medication of adverse events incidences within each MedDRA System Organ Class, and changes from pre-dose values in vital signs. Adverse event summaries will be presented by study medication showing the proportion of subjects experiencing adverse events, both overall and by MedDRA System Organ Class.

